### **11.5.5 Definition of an Overdose for This Protocol and Reporting of Overdose to the Sponsor and to Merck**

For purposes of this trial, an overdose of pembrolizumab will be defined as any dose of 1,000 mg or greater ( $\geq 5$  times the indicated dose). No specific information is available on the treatment of overdose of pembrolizumab. Appropriate supportive treatment should be provided if clinically indicated. In the event of overdose, the subject should be observed closely for signs of toxicity. Appropriate supportive treatment should be provided if clinically indicated.

*CONFIDENTIAL*

*This document is confidential. Do not disclose or use unless authorized.*

If an adverse event(s) is associated with (“results from”) the overdose of a Merck product, the adverse event(s) is reported as a serious adverse event, even if no other seriousness criteria are met.

If a dose of Merck’s product meeting the protocol definition of overdose is taken without any associated clinical symptoms or abnormal laboratory results, the overdose is reported as a non-serious Event of Clinical Interest (ECI), using the terminology “accidental or intentional overdose without adverse effect.”

All reports of overdose with and without an adverse event must be reported within 24 hours to the Coordinating Center and within 2 working days hours to Merck Global Safety. The Coordinating Center will submit all safety reports to Merck on behalf of the Sponsor.

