### **11.3 Serious Adverse Events**

A serious adverse event is any untoward medical occurrence at any dose or that:

- Results in death;
- Is life threatening;
- Results in persistent or significant disability/incapacity;
- Results in or prolongs an existing inpatient hospitalization;
- Is a congenital anomaly/birth defect;
- Is a new cancer (that is not a condition of the study);
- Is associated with an overdose;
- Is an important medical event

Refer to Table 6 for additional details regarding each of the above criteria.

Events **not** considered to be serious adverse events are hospitalizations for:

- routine treatment or monitoring of the studied indication, not associated with any deterioration in condition, or for elective procedures
- treatment planned before signing informed consent for a pre-existing condition that did not worsen
- emergency outpatient treatment for an event not fulfilling the serious criteria outlined above and not resulting in inpatient admission
- respite care
- Abnormal lab values that do not require medical intervention to return to baseline value

Progression of the cancer under study is not considered an adverse event unless it results in hospitalization or death.

All subjects with serious adverse events must be followed up for outcome.

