Seriousness	
A serious adverse event is any adverse event occurring at any dose or during any use of Merck product that:
 
†Results in death; or
 
†Is life threatening; or places the subject, in the view of the investigator, at immediate risk of death from the event as it occurred (Note: This does not include an adverse event that, had it occurred in a more severe form, might have caused death.); or
 
†Results in a persistent or significant disability/incapacity (substantial disruption of one's ability to conduct normal life functions); or
 
†Results in or prolongs an existing inpatient hospitalization (hospitalization is defined as an inpatient admission, regardless of length of stay, even if the hospitalization is a precautionary measure for continued observation. (Note: Hospitalization [including hospitalization for an elective procedure] for a preexisting condition which has not worsened does not constitute a serious adverse event.); or
 
†Is a congenital anomaly/birth defect (in offspring of subject taking the product regardless of time to diagnosis); or
 
Is a new cancer; (that is not a condition of the study) or
 
Is an overdose (whether accidental or intentional). Any adverse event associated with an overdose is considered a serious adverse event. An overdose that is not associated with an adverse event is considered a non-serious event of clinical interest and must be reported within 24 hours.
 
Other important medical events that may not result in death, not be life threatening, or not require hospitalization may be considered a serious adverse event when, based upon appropriate medical judgment, the event may jeopardize the subject and may require medical or surgical intervention to prevent one of the outcomes listed previously (designated above by a †).
							
Duration	Record the start and stop dates of the adverse event. If less than 1 day, indicate the appropriate length of time and units							
Action taken	Did the adverse event cause the Merck product to be discontinued?							

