### **11.5.4 Events of Clinical Interest**

Selected non-serious and serious adverse events are also known as Events of Clinical Interest (ECI) and must be recorded as such on the Adverse Event case report forms/worksheets and reported within 24 hours to the Coordinating Center and within 2 working days to Merck Global Safety. The Coordinating Center will submit all safety reports to Merck on behalf of the Sponsor.

---

*CONFIDENTIAL*

*This document is confidential. Do not disclose or use unless authorized.*

Events of clinical interest for this trial include:

1. An overdose of Merck product, as defined in Section 11.5.5 - Definition of an Overdose for This Protocol and Reporting of Overdose to the Sponsor, that is not associated with clinical symptoms or abnormal laboratory results.
2. An elevated AST or ALT lab value that is greater than or equal to 3X the upper institutional limit of normal and an elevated total bilirubin lab value that is greater than or equal to 2X the upper institutional limit of normal and, at the same time, an alkaline phosphatase lab value that is less than 2X the upper institutional limit of normal, as determined by way of protocol-specified laboratory testing or unscheduled laboratory testing.\*

*\*NOTE: These criteria are based upon available regulatory guidance documents. The purpose of the criteria is to specify a threshold of abnormal hepatic tests that may require an additional evaluation for an underlying etiology. The trial site guidance for assessment and follow up of these criteria can be found in the Investigator Trial File Binder (or equivalent).*

3. Additional adverse events:

A separate guidance document has been provided entitled “Event of Clinical Interest Guidance Document” (previously entitled, “Event of Clinical Interest and Immune-Related Adverse Event Guidance Document”). This document can be found in Appendix 4 and provides guidance regarding identification, evaluation and management of ECIs and irAEs.

ECIs (both non-serious and serious adverse events) identified in this guidance document from the date of first dose through 90 days following cessation of treatment, or 30 days after the initiation of a new anticancer therapy, whichever is earlier, need to be reported within 24 hours to the Coordinating Center and within 2 working days to Merck Global Safety regardless of attribution to study treatment, consistent with standard SAE reporting guidelines.

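### The trial-wide 1,000 mg overdose trigger in Section 11.5.5 is five times the dose only for a 200 mg dose, so for pediatric patients under 100 kg it is set too high by its own multiple

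*Combined protocol and SAP*

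**What the plan says.** Section 11.5.5 gives one definition: "For purposes of this trial, an overdose of pembrolizumab will be defined as any dose of 1,000 mg or greater". A parenthesis equates this with at least 5 "times the indicated dose". There is no pediatric or weight-based version.

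Several duties hang on the definition:

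- An adverse event resulting from an overdose is reported as serious "even if no other seriousness criteria are met".
- A symptom-free case becomes a non-serious event of clinical interest; this rule covers a dose "meeting the protocol definition of overdose is taken without any associated clinical symptoms or abnormal laboratory results".
- Every case carries a reporting clock: "All reports of overdose with and without an adverse event must be reported within 24 hours to the Coordinating Center". The limit for informing the manufacturer is 2 working days.
- The subject is to be watched closely for toxicity.

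Section 11.5.4, item 1, takes its meaning from the same place: "An overdose of Merck product, as defined in Section 11.5.5". Two other places use the word without a milligram figure. Section 11.3 counts an event as serious if it "Is associated with an overdose". Table 6 in Section 11.4 says: "Any adverse event associated with an overdose is considered a serious adverse event"; it also asks for a 24-hour report of an overdose with no adverse event.

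On dosing, Section 4.2.2 and the footnote to Table 2 in Section 7.1 set the pediatric dose at 2 mg/kg, capped at 200 mg. Section 5.1.2, item 2, allows entry from age 12 with assent, and Section 14.1 plans about 2-3 pediatric patients as an exploratory cohort.

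**The concern.** The definition consists of an absolute dose and a multiple, and the two agree only when the assigned dose is 200 mg. The protocol adapts the dose to pediatric patients but not the overdose trigger. Below 100 kg there is therefore a range of doses that are at least five times what the patient should have received, yet fall short of 1,000 mg.

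At stake is safety reporting after a gross dosing error in a minor. If the milligram figure governs, an error in that range does not start the 24-hour clock, does not become an event of clinical interest under 11.5.4 item 1, and does not make a resulting adverse event serious automatically under 11.5.5. The loss is clearest for an error without symptoms, where there may be no adverse event to bring it to attention, and for an associated event that is not serious on any other criterion.

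**Working it through.** **Inputs**

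- Trigger: 1,000 mg, described as at least 5 times the dose (Section 11.5.5).
- Adult dose: 200 mg every 3 weeks (Section 1.0; Section 7.1, Table 2).
- Pediatric dose: 2 mg/kg up to 200 mg (Section 4.2.2; Section 7.1, Table 2 footnote).
- Body weight w: assumed, 30 to 100 kg. The documents give no pediatric weights.

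**The plan's own figure.** For a 200 mg dose, 5 × 200 = 1,000 mg. It reproduces exactly.

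**Pediatric patients.** The assigned dose is d = min(2w, 200) mg, and five times it is 5d = min(10w, 1,000) mg. The two halves of the definition differ when 10w < 1,000, that is when w < 100 kg. The width of the uncovered range is 1,000 − 5d. The trigger expressed as a multiple of the assigned dose is 1,000/d.

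| Assumed weight (kg) | Assigned dose d (mg) | 5d (mg) | Uncovered width (mg) | 1,000/d |
|---|---|---|---|---|
| 30 | 60 | 300 | 700 | 16.7 |
| 40 | 80 | 400 | 600 | 12.5 |
| 50 | 100 | 500 | 500 | 10.0 |
| 60 | 120 | 600 | 400 | 8.3 |
| 70 | 140 | 700 | 300 | 7.1 |
| 90 | 180 | 900 | 100 | 5.6 |
| 100 | 200 | 1,000 | 0 | 5.0 |

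At 40 kg, for example, any dose from 400 mg to just under 1,000 mg is at least five times the assigned 80 mg but does not reach the trigger. In mg/kg the trigger there is 1,000/40 = 25, against an assigned 2. The range narrows with weight and closes at 100 kg.

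**How an error could get there.** The obvious slip is to give the flat adult dose. That is 200/60 = 3.3 times the assigned dose at 30 kg and 200/80 = 2.5 times at 40 kg, falling to 1.0 at 100 kg. It is below five at every weight shown, so it is not an overdose by either half of the definition. Reaching the uncovered range takes a larger mistake: with the 100 mg product in Section 15.1, Table 7, 400 mg at 40 kg is 400/100 = 4 units for a dose of 80 mg.

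**The case against.** The best defence is that Section 11.5.5 is clear. It fixes a number for the trial, and the parenthesis shows where the number comes from (5 × 200 mg). It is not a second test to be applied patient by patient, and 11.5.4 points back to that one number. This stands. A reader might infer that the section is ambiguous and that sites would therefore handle the same error differently. The documents do not support making that the main point, because the per-patient reading is the less natural one. What remains is a clear threshold that was not scaled to weight-based dosing and whose own description is untrue for most pediatric weights considered here.

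A second defence is that such an error would surface anyway. Much of this stands too. The general overdose wording in 11.3 and in Table 6 could prompt a report. Adverse events are recorded and judged on the other seriousness criteria. Section 11.5.1 covers unexpected events, and Sections 3.8.1 and 3.8.3 of the Data and Safety Monitoring Plan require departures from the protocol to be reported. A reader should therefore not infer that a pediatric overdose would go unreported. But violation reports are only required to be timely, with no 24-hour limit, and 11.5.1 needs a medical event. Neither reliably replaces the prompt report of a symptom-free error or the automatic serious classification.

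A third defence is that the low end of the range is not shown to be harmful. Section 4.2.2 reports that 10 mg/kg was well tolerated in the phase I trial, and that safety was similar at 2 and 10 mg/kg every 3 weeks in melanoma. That also stands: the documents do not support a claim that these doses are unsafe. Equally, the data described there do not go above 10 mg/kg and are not shown to be pediatric, so they do not cover the upper part of the range.

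Two smaller points. A per-dose trigger gives different limits at equal weight: at 70 kg, 700 mg for an adolescent but 1,000 mg for an adult. That follows from the multiple the protocol itself states. And Section 10.1.1.11 has administration witnessed and infused volume compared with prepared volume, which would not detect a dose prepared at the wrong amount.

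**Conclusion.** The point holds as a minor, lowest-priority safety-reporting correction. The 1,000 mg figure is not miscalculated; it is right for a 200 mg dose. For pediatric patients under 100 kg it exceeds five times the assigned dose, standing at about 7-fold at 70 kg and about 17-fold at 30 kg. On the natural reading, doses from 10 mg/kg to just under 1,000 mg fall outside the protocol definition and its consequences in 11.5.5 and 11.5.4 item 1.

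The reach is small. It concerns about 2-3 exploratory patients and matters only after a rare, gross dosing error. Adults, dosing and the efficacy analysis are unaffected.

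The conclusion rests on assumed weights for the size of the discrepancy, though not for its existence below 100 kg. It also rests on the visible text: the event-of-clinical-interest guidance and the pharmacy manual (Appendices E and I) are listed without content, so whether they add a pediatric rule cannot be checked. Section 11.5.4 refers only to 11.5.5 for what counts as an overdose.

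**What to change.** In Section 11.5.5 only, define overdose as any dose at least 5 times the subject's assigned dose: 1,000 mg or greater for adults, and 10 mg/kg or greater for pediatric patients, with the pediatric threshold capped at 1,000 mg.

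Nothing else needs editing. Section 11.5.4 item 1 already refers to 11.5.5, and 11.3 and Table 6 carry no milligram figure. Adult handling stays as it is. The cost is one clause and at most a few extra expedited reports, with no change to dosing, sample size or analysis.

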#### **11.5.6 Reporting of Pregnancy and Lactation to the Sponsor and to Merck**

Although pregnancy and lactation are not considered adverse events, it is the responsibility of treating investigators or their designees to report any pregnancy or lactation in a subject (spontaneously reported to them), including the pregnancy of a male subject's female partner that occurs during the trial or within 120 days of completing the trial completing the trial, or 30 days following cessation of treatment if the subject initiates new anticancer therapy, whichever is earlier. All subjects and female partners of male subjects who become pregnant must be followed to the completion/termination of the pregnancy. Pregnancy outcomes of spontaneous abortion, missed abortion, benign hydatidiform mole, blighted ovum, fetal death, intrauterine death, miscarriage and stillbirth must be reported as serious events (Important Medical Events). If the pregnancy continues to term, the outcome (health of infant) must also be reported.

Such events must be reported within 24 hours to the Coordinating Center and within 2 working days to Merck Global Safety. The Coordinating Center will submit all safety reports to Merck on behalf of the Sponsor.

#### **11.5.7 Sponsor Responsibility for Reporting Adverse Events**

All Adverse Events will be reported to regulatory authorities, IRB/IECs and investigators in accordance with all applicable global laws and regulations.

#### **11.5.8 Institutional Review Board (IRB) Notification by Investigator**

The participating investigator will report all adverse events and serious adverse events to the Coordinating Center and to the IRB according to the local IRB’s policies and procedures in reporting adverse events.

#### **11.5.9 Food and Drug Administration (FDA) Notification by Sponsor-Investigator**

The Overall PI, as study sponsor, will be responsible for all communications with the FDA. The Coordinating Center, on behalf of the Sponsor, will report to the FDA any adverse event that is serious, unexpected and reasonably related (i.e., possible, probable, definite) to the study treatment.

---

*CONFIDENTIAL*

*This document is confidential. Do not disclose or use unless authorized.*

Unexpected fatal or life-threatening experiences associated with the use of the study treatment will be reported to the FDA as soon as possible but in no event later than 7 calendar days after initial receipt of the information.

All other serious unexpected experiences associated with the use of the study treatment will be reported to the FDA as soon as possible but in no event later than 15 calendar days after initial receipt of the information.

Events will be reported to the FDA by telephone ([name]) or by fax ([name]) using Form FDA 3500A (Mandatory Reporting Form for investigational agents) or FDA Form 3500 (Voluntary Reporting Form for commercial agents). Forms are available at <http://www.fda.gov/medwatch/getforms.htm>.

#### **11.5.10 NIH Office of Biotechnology Activities (OBA) Notification by Investigator**

Not applicable

#### **11.5.11 Institutional Biosafety Committee (IBC) Notification by Investigator**

Not applicable

#### **11.5.12 Hospital Risk Management Notification by Investigator**

The participating investigator will report to the Coordinating Center and to local Risk Management any subject safety reports or sentinel events that require reporting according to institutional policy.

### **11.6 Routine Adverse Event Reporting**

All Adverse Events **must** be reported in routine study data submissions to the Overall PI on the toxicity case report forms. **AEs reported through expedited processes (e.g., reported to the IRB, FDA, etc.) must also be reported in routine study data submissions.**

## **12.0 DATA AND SAFETY MONITORING**

### **12.1 Data Reporting**

#### **12.1.1 Method**

The DF/HCC Office of Data Quality (ODQ) will collect, manage, and audit data for this study.

### 12.1.2 Data Submission

The schedule for completion and submission of case report forms (paper or electronic) to the ODQ is as follows:

Form	Submission Timeline
Eligibility Checklist	Complete prior to registration
On Study Form	Within 14 days of registration
Baseline Assessment Form	Within 14 days of registration
Treatment Form	Within 10 days of the last day of the cycle
Adverse Event Report Form	Within 10 days of the last day of the cycle
Response Assessment Form	Within 10 days of the completion of the cycle required for response evaluation
Off Treatment/Off Study Form	Within 14 days of completing treatment or being taken off study for any reason
Follow up/Survival Form	Within 14 days of the protocol defined follow up visit date or call

### 12.2 Data Safety Monitoring

The DF/HCC Data and Safety Monitoring Committee (DSMC) will review and monitor toxicity and accrual data from this trial. The committee is composed of clinical specialists with experience in oncology and who have no direct relationship with the study. Information that raises any questions about participant safety will be addressed with the Principal Investigator and study team.

The DSMC will meet approximately quarterly and/or more often if required to review toxicity and accrual data. Information to be provided to the committee may include: up-to-date participant accrual; current dose level information; all grade 2 or higher unexpected adverse events that have been reported; summary of all deaths occurring within 30 days for Phase I or II protocols; summary of all deaths while being treated and during active follow-up; any response information; audit results, and a summary provided by the study team. Other information (e.g. scans, laboratory values) will be provided upon request.

### 12.3 Multi-center Guidelines

This protocol will adhere to the policies and requirements of the DF/HCC Multi-Center Data and Safety Monitoring Plan. The specific responsibilities of the Overall PI, Coordinating Center, and Participating Institutions and the procedures for auditing are presented in Appendix I.

- The Overall PI/Coordinating Center is responsible for distributing all IND Action Letters or Safety Reports to all participating institutions for submission to their individual IRBs for action as required.
- Mechanisms will be in place to ensure quality assurance, protocol compliance, and adverse event reporting at each site.

*CONFIDENTIAL*

*This document is confidential. Do not disclose or use unless authorized.*

- Except in very unusual circumstances, each participating institution will order the study agent(s) directly from supplier. A participating site may order the agent(s) only after the initial IRB approval for the site has been forwarded to the Coordinating Center.

## 12.4 Monitoring

Involvement in this study as a participating investigator implies acceptance of potential audits or inspections, including source data verification, by representatives designated by the Principal Investigator (or Protocol Chair) or DF/HCC. The purpose of these audits or inspections is to examine study-related activities and documents to determine whether these activities were conducted and data were recorded, analyzed, and accurately reported in accordance with the protocol, institutional policy, Good Clinical Practice (GCP), and any applicable regulatory requirements.

All data will be monitored for timeliness of submission, completeness, and adherence to protocol requirements. Monitoring will begin at the time of participant registration and will continue during protocol performance and completion.

## 13.0 REGULATORY CONSIDERATIONS

### 13.1 Protocol Review and Amendments

This protocol, the proposed informed consent and all forms of participant information related to the study (e.g., advertisements used to recruit participants) and any other necessary documents must be submitted, reviewed and approved by a properly constituted IRB governing each study location.

Any changes made to the protocol must be submitted as amendments and must be approved by the IRB prior to implementation. Any changes in study conduct must be reported to the IRB. The Principal Investigator (or Protocol Chair) will disseminate protocol amendment information to all participating investigators.

All decisions of the IRB concerning the conduct of the study must be made in writing.

